4.0 Eligibility Criteria

4.1 Inclusion Criteria

- 25 years and older
- Ability to provide informed consent

- Undergoing colonoscopy for screening, surveillance, diagnostic reasons, or removal of a lesion

4.2 Exclusion Criteria

- Pedunculated lesions
- Inflammatory bowel disease
- Inability to provide informed consent
- Lesions less than 15mm in largest dimension

5.0 Study Design and procedures

A member of the research team will approach a potential subject to discuss participation in the study, including background of the proposed study, inclusion and exclusion criteria, benefits and risks of the procedures and follow-up. If this is of interest to the subject, the informed consent document will be discussed and presented. The subject must sign the consent form prior to enrollment. This form will have prior approval of the study site's Institutional Review Board (IRB). Failure to obtain informed consent renders the subject ineligible for the study.

Patients who have provided informed consent and are scheduled to undergo endoscopic mucosal resection (EMR) of lesions 15mm and larger will be enrolled in the study. During the procedure randomization will be performed by approved study staff once the colonoscopist confirms the eligibility (at least one sessile polyp greater than 15 mm in the largest dimension measured by the snare size). The three arms of randomization are STSC (80 W, Effect 5) vs APC (preferred settings) vs No Treatment of the perimeter of the EMR site. The randomization list,

which will include 645 randomized treatments, will be generated by our biostatistics department by [name]. These selections will then be printed and placed into sealed envelopes pertaining to the patient numbers and will be opened following confirmation that the patient is study eligible. Randomization will occur on a per procedure basis.

All randomized subjects will receive a 30-day post procedure follow-up phone call (+ 7 days) and be scheduled, as per the standard of care, to receive a standard follow-up colonoscopy procedure after the initial procedure. The follow-up window for the primary endpoint has been extended beyond 6 months due to procedure delays caused by the COVID-19 pandemic. We will measure the rate of recurrence by endoscopic visualization of the EMR site at the first follow-up using endoscopic magnification and electronic chromoendoscopy, as well as systematic biopsy of the scars. Additionally we will look for the presence of scarring and any clips retained.

6.0 Enrollment/Randomization

All colonoscopies in the study will be performed by [name] or one of the Sub-Investigators listed above. Patients will be 25 and older and will be randomized to one of the aforementioned arms of the study. Blinding of the PI will be maintained until the end of the polypectomy procedure at the primary procedure. Further blinding is not possible due to the nature of the study.

Screen failure: any patient enrolled in the study but not randomized because of not satisfying polyp size or other exclusion criteria discovered during the procedure.

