3.2 Secondary Outcome Measures

Time it takes to apply each treatment will be recorded by a research assistant during the index procedure using a stop watch. During the colonoscopy the

treatment time will be recorded as the time, after initial polyp resection, that the randomized treatment instrument comes into view until before clips are applied. Complications will be assessed during the follow-up call simply by asking the patients if they experienced any adverse events. We will use the following definitions to ascertain complications:

Bleeding: severe bleeding event that required hospitalization, a blood transfusion, a colonoscopy, surgery, or any other invasive intervention to control bleeding, and that occurred after the patient left the endoscopy unit and within 30 days after completion of the colonoscopy

Perforation: iatrogenic full thickness defect in the colon wall diagnosed within two weeks of the procedure

Pain: Any pain perceived by the patient after they left the endoscopy unit and within 30 days after completion of the colonoscopy

Post polypectomy syndrome: Abdominal pain, fever, leukocytosis and peritoneal inflammation in the absence of perforation within two weeks of the procedure

Our cost analysis will then take all of these endpoints into account to report which method we found to be more affective. As stated, this will be based on the instrument cost, treatment time, polyp recurrence, and reported complications.

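### Section 6.0 rules out all blinding after the polypectomy, but nothing in the plan requires the patient or the 30-day caller to know the arm, and leaving them unblinded can bias self-reported pain

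*Combined protocol and SAP*

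**What the plan says.** Section 6.0 gives the whole blinding plan in two sentences: "Blinding of the PI will be maintained until the end of the polypectomy procedure at the primary procedure", followed by "Further blinding is not possible due to the nature of the study". No role other than the PI is discussed.

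Section 5.0 says when the arm becomes known: "During the procedure randomization will be performed by approved study staff once the colonoscopist confirms the eligibility". The sealed envelopes "will be opened following confirmation that the patient is study eligible". The arms are STSC "vs APC (preferred settings) vs No Treatment of the perimeter of the EMR site".

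Section 3.2 describes ascertainment: "Complications will be assessed during the follow-up call simply by asking the patients if they experienced any adverse events". It defines pain as "Any pain perceived by the patient after they left the endoscopy unit", up to 30 days after the colonoscopy. No scale, severity threshold or question list is given. Section 7.0 places the call at day 30 (+ 7 days). If the call fails, it accepts complication information collected at the first follow-up.

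Section 11.0 compares the number of complications among the arms by negative binomial regression.

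**The concern.** The blanket statement treats everyone as if they were in the operator's position. The endoscopist must know the arm in order to deliver it. The patient and the caller have no such task, and the plan describes no measure to keep either unaware. A site that follows Section 6.0 as written has no reason to withhold the arm from anyone.

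Pain is the component most exposed. A patient who knows that thermal treatment was added may report discomfort that would otherwise go unmentioned. A caller who knows the arm may probe harder in treated patients. Because the control receives no perimeter treatment, both effects can differ between arms. What is at stake is the interpretation of a secondary outcome: a difference in complications that is driven by pain could reflect reporting rather than APC or STSC.

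**Working it through.** **Who needs to know the arm, by the plan's own procedures**

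| Role | Contact with the arm | Must know it? |
|---|---|---|
| Treating endoscopist, room staff | Envelope opened and treatment given during the procedure (5.0) | Yes |
| Patient | Treatment or no treatment of the resection margin within one colonoscopy (5.0) | No step described requires it |
| 30-day caller | Separate phone contact, day 30 + 7 (7.0) | No step described requires it |
| Person collecting complications at first follow-up if the call failed | Fallback in 7.0 | No step described requires it |

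**Which components are open to reporting bias (3.2)**

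- Pain: patient perception alone, no threshold. Fully exposed.
- Bleeding: requires hospitalization, transfusion or an intervention. Little exposed.
- Perforation: a diagnosed full-thickness defect. Little exposed.
- Post polypectomy syndrome: includes fever, leukocytosis and peritoneal inflammation. Less exposed than pain.

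**Illustration of size**

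The plan gives no pain rate, so there is no figure to reproduce. The base rates and reporting shifts below are assumptions.

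Inputs: 380 patients randomized 1:1:1 (11.0), so 380/3 = 126.7, taken as n = 126 per arm with no loss; equal true pain rates; two-sided 5% test, z = 1.96. Let p₁ be the reported rate without awareness, p₂ the rate with it, p̄ their mean and d = p₂ − p₁.

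- s₀ = √[2p̄(1 − p̄)/n]
- s₁ = √{[p₁(1 − p₁) + p₂(1 − p₂)]/n}
- P(falsely significant) = Φ[(d − 1.96 s₀)/s₁] + Φ[(−d − 1.96 s₀)/s₁]

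For 20% against 25%: p̄ = 0.225, s₀ = 0.0526, s₁ = 0.0525. The two arguments are −1.011 and −2.916, giving 0.156 + 0.002 = 0.158.

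| Reported pain, unaware v aware | n = 126 per arm | n = 115 per arm |
|---|---|---|
| 20% v 25% | 0.158 | 0.148 |
| 20% v 30% | 0.449 | 0.417 |
| 10% v 15% | 0.224 | 0.208 |

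The second column of results uses the 115 per arm on which the plan is powered (3 × 115 + 35 = 380). The choice of n matters little.

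These are error rates for a pain-only comparison of one treated arm with control. The planned test is a negative binomial model of the complication count, in which pain is one contributor. The figures show only that a modest reporting shift could matter; they are not error rates of the planned analysis.

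**The case against.** The strongest reply has five parts.

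*The harm is conjecture.* The plan does not tell sites to disclose the arm, does not say who makes the call, and does not say whether the call sheet shows the allocation. The consent pages are not available for review. This stands as far as it goes: the documents support saying that the plan can bias reported pain, not that it does. But Section 6.0 is more than silent. It states that no further blinding is possible, and so removes the reason to try.

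*Most complications are hard endpoints.* This stands. A reader might infer that no arm difference in complications could be attributed to treatment. The definitions of bleeding, perforation and post polypectomy syndrome do not support that; the concern is mainly pain, and the total count through pain.

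*The cost analysis is not affected in the same way.* A reader might infer that a treated-versus-untreated reporting bias carries into it, since Section 3.2 lists reported complications among its inputs. Section 11.0, however, compares costs only between APC and STSC. Both involve thermal treatment of the margin, so an expectation effect would be largely shared. The documents do not support that consequence.

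*The error rates model a different test with assumed inputs.* This stands, and they are used here only as illustration.

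*Feasibility is inferred.* The plan gives no sedation level, and some patients may learn the arm from their records. Imperfect blinding is still better than none, provided that awareness is recorded.

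**Conclusion.** The point holds in limited form. The statement in Section 6.0 is right for the treating endoscopist and room staff, and too broad for the patient and the person collecting complications. Leaving those two unblinded can bias self-reported pain in the comparison of APC or STSC with no treatment, and so the complication count.

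Size and direction are unknown. Under the assumed reporting shifts, a simple pain-only test would be falsely significant in about 16% to 45% of trials at n = 126 per arm, against a nominal 5%. That range depends entirely on the assumed rates.

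The outcome is secondary, and the sample size of 380 is unaffected. The change is worth making because the bias is avoidable at low cost. This point does not address who reads the scar at the follow-up colonoscopy.

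**What to change.** Revise Section 6.0, with matching wording in 3.2 and 7.0:

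1. Limit the statement that blinding is not possible to the treating endoscopist and room staff.
2. State that the patient is not told the allocation until the follow-up colonoscopy is complete, unless it is needed for care.
3. Have complications collected by an existing coordinator who was not in the procedure room, using a fixed question list that does not show the arm. Apply this both to the 30-day call and to collection at first follow-up when the call failed.
4. Record at the end of each contact whether the patient or the coordinator knew the arm, and report this by arm.

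Cost: protocol and consent wording, a short question list and one CRF item, with existing staff. Some patients will still learn the arm from their procedure report, and small sites may have to swap who calls. The COVID-19 follow-up extension in 5.0 and the additional number blocks in 11.0 suggest that recruitment had already begun. Patients already enrolled will then have been followed under the old rule, so the report should state how many were followed under each.

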7.0 Study Calendar

Index procedure will be the day of colonoscopy where one of the intervention arms or the control arm is administered. Patients will receive a follow-up phone call at 30-days (+ 7 days) to ascertain any complications as previously described. Patients will also receive a follow-up colonoscopy (standard of care for large polyp removal) where the polypectomy site is observed for any recurrence.

	Index procedure	Follow-up phone call	Follow-up colonoscopy
	Day 1	Day 30 + 7 days	Approximately Day 180
Study Procedures	Colonoscopy with one of the intervention arms or control	Phone call to ascertain complications	Colonoscopy to observe for recurrence at polypectomy site

Lost to follow-up: All patients who are randomized to one of the interventions but fail to complete the required follow-up colonoscopy. Failure to contact at 30 days will not be considered lost to follow-up (complications information in such cases will be deemed acceptable if collected at the first follow-up but an accurate accounting of the number of such patients will be kept and reported to the DSMB).

8.0 Reportable Events

All adverse events meeting prompt reporting criteria will be reported to the IRB within 5 business days of the study team becoming aware of the event. An adverse event meeting prompt

reporting criteria for this study is defined as any event assessed by the PI, or appropriately trained and qualified designee, as (1) unexpected, (2) related or possibly related to study participation, AND (3) suggesting that the research places subjects or others at greater risk of harm than was previously known. The period for assessing AE's will be from the point of inserting the colonoscope until 30 days after the index colonoscopy.

9.0 Data Safety Monitoring

See Data and Safety Monitoring Board Charter for information about DSMB. Briefly, the data safety monitoring board comprises 4 members: [name] MD (Indiana University), [name] PhD (Indiana University), [name] MD (Henry Ford Hospital), and [name] MD (Chair), (Medical University of South Carolina). None of the board members are involved with the current study in any capacity. Additionally, [name] research team will provide him up to date information regarding the status of patients and any reportable events.

The data collected at sites other than IU will be de-identified before being sent to us. Each site will enter their data in to a secure web application (REDCap), which will then be accessed at the primary site. Only de-identified data from external sites will be added to the database (no HIPAA identifiers will be collected from external sites besides procedure dates and de-identified images of study lesions). Any other communication that is not patient related will be done over email or phone.

Variables that will be transmitted from the other site include:

- Information from the procedure to remove the large polyp
 - This includes information about meeting inclusion/exclusion criteria, procedure date, randomization envelope number/randomization treatment, age, gender, race,

ethnicity, whether a fellow was involved in the procedure (and which parts of procedure, if applicable), procedure times, study polyp characteristics, de-identified study lesion images, resection times, information about the resection such as snare/ injection fluid usage and number of resected pieces, treatment times, other additional treatments used, clipping times, number/type of clips used, type of colonoscope used, Boston Bowel Preparation Score, whether fibrosis was present, whether there were any prior attempts at resection, information about procedural complications (if any), and study polyp pathology results

- Information from the 30 day follow up call
 - This includes information about whether the follow-up phone call was made successfully, date subject was reached by phone, and whether patient reported experiencing adverse events (and if so, information about the adverse event).
 - Information from the first follow-up procedure
 - This includes information about the previous EMR site, date of follow-up procedure, pathology results from residual or recurrent polyp tissue found at previous EMR site (if applicable), and pathology results from biopsies obtained from previous EMR site

10.0 Study Withdrawal/Discontinuation

Any subject who wishes to withdraw from this investigation on his/her own accord and for whatever reason is entitled to do so without obligation and prejudice to further treatment. In addition, the Investigator may decide for reasons of medical prudence, to withdraw a subject. In either event, the Investigator will clearly document the date and reason(s) for the subject's

withdrawal from this investigation in the CRF and should indicate whether or not he considers it was related to the study interventions.

11.0 Statistical Considerations

Assuming a 25% recurrence rate of the control arm, and a reduction to 10% in both of the treatment arms, we estimate that a sample size of 115 subjects per arm will be needed to demonstrate that APC and STSC are superior to no treatment for reduction of recurrence rate after EMR, based on 80% power and a two-sided 5% significance level for comparison of independent proportions with one interim analysis. The no treatment arm will be used as our control. In order to account for drop-outs, an extra 35 patients will be enrolled into the study to ensure sufficient data will be included in the analysis. Therefore, a sample size of 380 subjects will be enrolled in this study.

Once a polyp has been identified and its size fits within the targeted range, each subject will be randomized in a 1:1:1 ratio using a computer generated randomization sequence. Enrollment into the study will be competitive with the possibility for each site outside of IU to randomize up to 100 patients. Not all 645 randomization numbers generated will be used in the study. Instead each external site will continue to enroll until a total of 380 patients have been randomized study-wide with a potential to randomize up to 100 patients. Randomization numbers will be assigned as follows: IU will be assigned numbers 001 – 095 and 496 - 526; AdventHealth Orlando will be assigned 096 – 145 and 446 - 470; The Johns Hopkins Hospital will be assigned numbers 146 – 195; Dartmouth-Hitchcock Medical Center will be assigned numbers 196 – 245; NYU Langone Medical Center will assigned numbers 246 – 295 and 471 - 495; the Mount Sinai

Hospital will be assigned 296 – 345, Sibley Memorial Hospital will be assigned 346 – 395, the University of Kansas Medical Center will be assigned 396 – 445, and Penn State Health Milton S. Hershey Medical Center will be assigned 546 - 595. The proportion of subjects with recurrence will be compared between study arms using chi-square tests. The number of complications will be compared among treatment arms using negative binomial regression. Treatment times and costs will be compared between the APC and STSC arms using Wilcoxon Rank Sum tests. A 5% significance level will be used for all tests.

Interim analysis and stopping rule:

The interim analysis will be conducted after half of the subjects have completed the study, using an O'Brien-Fleming spending function with alpha levels 0.003 and 0.049 at the interim and final analyses. Any results will be considered significant at a p-value of ≤ 0.003 at the interim analysis and the DSMB will make a decision about stopping the study based on those results.

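### Randomization numbers are issued site by site, but the recurrence test ignores site: a modest loss of precision and calibration that a site-stratified test would recover

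*Combined protocol and SAP*

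**What the plan says.** Allocation is organised by site. Section 11.0 states that "each subject will be randomized in a 1:1:1 ratio using a computer generated randomization sequence", and then lists a range or ranges for each of nine sites, beginning "Randomization numbers will be assigned as follows: IU will be assigned numbers 001 – 095 and 496 - 526". Section 5.0 ties the envelopes to those numbers: "These selections will then be printed and placed into sealed envelopes pertaining to the patient numbers". Each site therefore works through its own part of the list. Neither section mentions blocks or stratification factors.

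Site sizes are left open: "Enrollment into the study will be competitive with the possibility for each site outside of IU to randomize up to 100 patients".

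The analysis has no counterpart to this structure. For recurrence, section 11.0 says only "The proportion of subjects with recurrence will be compared between study arms using chi-square tests". Site appears nowhere in the protocol as a stratum, covariate, random effect or sensitivity analysis.

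**The concern.** A trial is normally analysed by the groups within which it allocated. If envelopes are balanced within site, the allocation removes between-site differences in recurrence from the treatment contrast. A pooled chi-square still counts those differences in its variance. Its standard error is then too large, its true error rate falls below nominal, and some available power goes unused.

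There is reason to expect sites to differ. Operators and case mix will vary, section 9.0 records fellow involvement and details of the resection, and the timing of the follow-up colonoscopy was loosened during the pandemic (section 5.0). At stake is the precision and calibration of the primary comparison.

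**Working it through.** **1. The plan's own figure.** Inputs from section 11.0: "Assuming a 25% recurrence rate of the control arm, and a reduction to 10% in both of the treatment arms", 80% power, two-sided 5%, 115 per arm.

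n = [z(α/2)·√(2p̄q̄) + z(β)·√(p₁q₁ + p₂q₂)]² / d², with p̄ = 0.175 and d = 0.15

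= [1.960·√0.28875 + 0.842·√0.2775]² / 0.0225 = 99.5, so 100 per arm.

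With continuity correction, n′ = (n/4)·[1 + √(1 + 4/(n·d))]² = 112.5, so 113 (114 at α = 0.049). The stated 115 is reproduced to within 3%, and 3 × 115 + 35 = 380. The calculation contains no site term. Because the correction adds patients, an uncorrected test with 115 per arm has about 85% power at level 0.049.

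**2. Number ranges.** One site holds 95 + 31 = 126 numbers, two hold 50 + 25 = 75, and six hold 50. The total is 126 + 150 + 300 = 576 of 645.

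**3. The two tests compared.**
- Pooled: z = (p̂_C − p̂_T) / √[p̄(1 − p̄)(1/n_C + 1/n_T)].
- Site-stratified (Cochran-Mantel-Haenszel, CMH): z = Σ(x_Cs − n_Cs·M_s/N_s) / √Σ[n_Cs·n_Ts·M_s(N_s − M_s) / (N_s²(N_s − 1))], where N_s and M_s are the patients and recurrences in the two compared arms at site s.

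The simulation used one active arm against control, 115 analysed per arm, nine sites sized in proportion to their numbers, level 0.049, no continuity correction, and 20,000 runs per setting. Site intercepts were normal on the logit scale, recalibrated at each SD so that average recurrence stayed at 25% v 10%. The SD is assumed. Monte Carlo standard errors are √(0.86 × 0.14/20,000) = 0.25 points for power and √(0.038 × 0.962/20,000) = 0.14 points for error rate.

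| Site SD | Control rate, middle 80% of sites | Balanced within site: power, pooled v CMH | Error rate, pooled v CMH | Simple allocation: power, pooled v CMH | Error rate, pooled v CMH |
|---|---|---|---|---|---|
| 0 | 25% | 86.4% v 85.9% | 4.9% v 5.0% | 85.9% v 84.4% | 5.1% v 5.1% |
| 0.5 | 14–37% | 86.4% v 86.7% | 4.6% v 5.0% | 86.1% v 85.7% | 5.2% v 5.2% |
| 0.8 | 9–45% | 86.1% v 87.4% | 3.8% v 4.6% | 86.2% v 87.1% | 4.8% v 4.8% |
| 1.0 | 7–49% | 86.8% v 88.7% | 3.5% v 4.9% | 85.5% v 87.6% | 5.1% v 5.0% |

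**4. A second assumption about site sizes.** With 96 patients at one site and 31 at each of eight (96 + 8 × 31 = 344), balanced within site, CMH changes power by −0.1, +0.5, +1.4 and +2.3 points at SD 0, 0.5, 0.8 and 1.0. The pooled error rate falls from 5.0% to 3.7%, and CMH stays at 4.6–5.0%. Under simple allocation the pooled test holds at 4.7–5.2%. The two layouts agree apart from small differences, largely simulation error.

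**The case against.** The strongest defence is that nothing invalid happens. A conservative test cannot raise the false-positive rate, the unadjusted chi-square matches the basis of the sample size, and every scenario exceeds 80% power. The larger gains need wide variation: at SD 0.5, where control rates already span about 14–37% over the middle 80% of sites, the gain is half a point or less. If the list is not blocked and sites are alike, CMH is slightly worse. All of this stands. It limits the size of the point but does not remove the mismatch between allocation and analysis.

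Three stronger readings are tempting and not supported:

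- *Site variation erodes the planned power.* A simulation that fixes 25% and 10% at the typical site shows pooled power falling from 85.6% to 82.8% as the SD rises to 1.0. Average recurrence has then drifted to about 28.5% v 13.4%, which is not the trial that section 11.0 assumes. With the averages held, pooled power stays near 86%.
- *Imbalance between sites biases the comparison.* Under simple allocation, chance imbalance is already covered by the test's error rate. Range lengths that do not divide by three would leave a blocked list uneven by only a patient or two per range.
- *Stratifying deals with differences in how treatment is delivered.* Section 5.0 describes one arm only as "APC (preferred settings", so the APC effect may vary by site. CMH estimates a common effect and does not test that. With about 31/3 ≈ 10 patients per arm at a typical external site, an arm-by-site table can only describe.

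**Conclusion.** The point holds as a modest one about precision and calibration. The size of the conservatism and of the gain in power depends on three assumptions: balance within site, which the protocol does not document; a site SD, for which it gives no figure; and a chi-square without continuity correction, which it does not specify. The check covers one comparison with control at the stated final level and does not model the interim look. The protocol supports no claim of bias, inflated error or power below plan.

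**What to change.** In section 11.0, replace the pooled chi-square for each recurrence comparison (APC v control, STSC v control) with a Cochran-Mantel-Haenszel test and a Mantel-Haenszel common risk difference, both stratified by site. In the same paragraph:

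- say whether the list is blocked within site;
- give a rule, fixed before the interim, for pooling sites with very few patients;
- use the same test at the interim and final looks;
- keep the unadjusted chi-square as a sensitivity analysis;
- label any arm-by-site table of recurrence as descriptive.

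The cost is wording only, since the number ranges already identify the site. The price in power, if sites do not differ, runs from almost nothing with balance within site to about 1.5 points under simple allocation.

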2.0 Objective(s)

2.1 Primary Objective

To investigate the efficacy of APC or STSC in reducing the recurrence rate at the first follow-up after polypectomy of large colon polyps

Hypothesis:

APC or STSC treatment of the perimeter of the EMR defect will reduce the recurrence rate of adenomas when compared to our control of no treatment.

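### APC and STSC are each tested against the shared control at the full two-sided 5% under one either-or hypothesis, with no multiplicity rule across arms: two-sided family-wise error is about 9% with uncorrected chi-square tests

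*Combined protocol and SAP*

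**What the plan says.** Section 2.1 gives one hypothesis, that "APC or STSC treatment of the perimeter of the EMR defect will reduce the recurrence rate of adenomas" relative to no treatment. On that wording, success with either treatment supports it.

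Section 11.0 sizes the trial on two-proportion comparisons with a shared control: "Assuming a 25% recurrence rate of the control arm, and a reduction to 10% in both of the treatment arms", with 115 per arm, "based on 80% power and a two-sided 5% significance level for comparison of independent proportions with one interim analysis". It adds "The no treatment arm will be used as our control". The analysis sentence is "The proportion of subjects with recurrence will be compared between study arms using chi-square tests". It lists no pairs and does not say whether a continuity correction applies. The section sets 5% as the level for all tests.

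The interim paragraph of section 11.0 specifies an O'Brien-Fleming spending function with "alpha levels 0.003 and 0.049 at the interim and final analyses", and treats any result at or below 0.003 at the interim as significant.

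The document contains no hierarchy, gatekeeping, closed test or division of alpha between the two treatments.

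**The concern.** The interim boundaries control the error from looking twice at one comparison. They do nothing about having two treatments, either of which can carry the primary hypothesis. Each control comparison receives the whole 5%, so the chance that at least one is significant when neither treatment has an effect exceeds 5%.

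Section 1.0 presents the trial as the one that will settle whether these treatments work, because the earlier evidence was small or non-randomized. A primary claim resting on whichever of two tests succeeds, each at full alpha, is open to challenge at publication. The rule is also easier to fix before the data are seen than to defend afterwards.

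**Working it through.** **Inputs.** From section 11.0: recurrence 25% (control) and 10% (each treatment), 115 evaluable per arm, 1:1:1 allocation, two-sided 5%, looks at 0.003 and 0.049. Assumed: the interim falls at half information, 58 per arm (115/2 = 57.5, rounded up), and a rejection at either look counts.

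**1. The plan's sample size.** With mean proportion 0.175,

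n = [1.960·√(2·0.175·0.825) + 0.842·√(0.25·0.75 + 0.10·0.90)]² / 0.15² = 99.5, so 100 per arm.

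With continuity correction, n′ = (n/4)·[1 + √(1 + 4/(n·0.15))]² = 112.5, so 113. At alpha 0.049 the two results are 101 and 114. The plan's 115 is close to the corrected figure, and 3 × 115 + 35 = 380. Each comparison is therefore sized at its own 5%.

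**2. One comparison over two looks.** Levels 0.003 and 0.049 at half information give an overall two-sided error of 0.04998. The spending is correct for a single comparison.

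**3. Two comparisons sharing a control.** With equal arms the two test statistics have correlation 0.5. Under no effect:

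- Either direction: P(at least one) = 0.05 + 0.05 − P(both) = 0.10 − 0.0093 = 0.0907.
- Benefit only: 0.025 + 0.025 − 0.0046 = 0.0454, against 0.025 for one comparison, a ratio of about 1.8.

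**4. Simulation with the planned looks.** 400,000 trials per scenario, binomial outcomes, pooled-variance tests. Error under no effect:

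| Pairwise test | Null recurrence | Either control comparison, two-sided | Any of three pairs, two-sided | False benefit, at least one |
|---|---|---|---|---|
| Uncorrected | 25% | 9.1% | 12.2% | 4.6% |
| Uncorrected | 10% | 9.0% | 12.1% | 4.5% |
| Continuity-corrected | 25% | 6.4% | 8.8% | 3.2% |
| Continuity-corrected | 10% | 5.0% | 7.0% | 2.5% |

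**5. The closed test.** With three arms, if any two pairwise null hypotheses are true, all three arms are equal. The only intersection to test is therefore the global null. A three-arm chi-square gate followed by pairwise tests at the same level is a closed procedure. With uncorrected tests, the simulated error for any pair is 4.8 to 5.1%, and for the two control comparisons 4.0 to 4.2%.

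**6. Power at 115 per arm.**

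| Quantity | No gate | With gate |
|---|---|---|
| Per comparison, both work | 86.5% | 84.1% |
| Its power, only one works | 86.5% | 82.4% |
| At least one, both work | 94.7% | 90.2% |
| Both shown superior | 78.3% | 78.1% |
| Per comparison, both work, corrected pairwise tests | 81.8% | 80.7% |
| Its power, only one works, corrected pairwise tests | 81.7% | 79.5% |

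For comparison, Bonferroni at 0.025 gives (0.15 − 2.241·√(2·0.175·0.825/115)) / √(0.2775/115) = 0.77, or about 78% power per comparison.

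**The case against.** The strongest case against is that APC and STSC are distinct treatments, each with its own question, and that sharing a control does not by itself oblige a trial to adjust. Statisticians do differ on this, and the document never promises a family-wise 5%; its 5% is a level per test. Section 11.0 also describes the sample size as that needed to show both treatments superior. If success required both, no adjustment would be needed. These points stand as reasons why the omission is not an outright error. They weigh less here because section 2.1 states a single either-or claim, and because the plan neither defines success as both nor says that the comparisons are to be read separately.

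The size also depends on an unstated choice. With continuity-corrected tests, which the 115 per arm most nearly matches, the two-sided family-wise error is only about 5 to 6%.

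Three stronger readings are tempting and are not supported:

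- A reader might infer a 9% chance of falsely claiming that a treatment works. The 9% includes treatments that look worse than control; the false-benefit figure is about 4.6%.
- A reader might take the 9% as the error over every pair. It covers the two control comparisons only. Section 11.0 names APC v STSC explicitly only for times and costs; testing that pair for recurrence as well gives about 12%.
- A reader might infer that the remedy keeps all power above 80%. That holds per comparison with uncorrected tests. It fails narrowly (79.5%) with corrected tests if only one treatment works, and power to show both superior is about 78% with or without the gate.

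**Conclusion.** The point holds: the plan handles multiplicity over looks but not over treatments. With uncorrected chi-square tests at 115 per arm, two-sided family-wise error is about 9% for the two control comparisons, and the false-benefit error is about 1.8 times that of a single comparison. These figures assume equal arms, an interim at half information, pairwise testing against control (inferred from the sizing, since no pairs are listed) and success on either arm. They barely change between 25% and 10% null recurrence for uncorrected tests, and shrink under continuity correction. This is a worthwhile improvement at small cost, not a flaw that invalidates the design.

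**What to change.** Add to section 11.0, before any unblinded comparison of the arms:

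> Pairwise recurrence tests are interpreted only if the three-arm chi-square test (2 df) is significant at the level for that look (0.003 interim, 0.049 final). Each pairwise test then uses the chi-square test without continuity correction at that same level.

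List the pairs to be tested, and reconcile the general 5% level with the final level of 0.049.

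The cost is one extra test and no more patients. Power per comparison falls by about 2 points if both treatments work and about 4 if only one does. Power for at least one success falls by about 4.5 points, to about 90%, and power for both is essentially unchanged at about 78%. If corrected pairwise tests are preferred, the 79.5% case should be acknowledged.

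If the sponsor prefers no adjustment, the plan should say so, give the reason, and state whether success means either treatment or both.
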